11.0 Data Management

11.a. Data Analysis Plan for Primary Endpoint. The primary endpoint is BIS scores measured at specific time points (Figure 3). We will summarize BIS at each time point by estimating mean and corresponding 95% confidence intervals (CIs), median, standard deviation (SD), inter-quartile range, and range. We will also construct boxplots and spaghetti plots of serially collected BIS scores to provide visual assessment of temporal changes in BIS. Finally, we will analyze BIS scores over time using linear mixed effects (LME) regression models with time as a fixed effect (considered as categorical variable) and subject-specific random effects to account for the correlation among measures obtained from the same subject over time. We will consider transformations for BIS scores to induce approximate normality and stabilize variance. BIS comparisons over time will be conducted using model-based linear contrasts. We will also consider Wilcoxon sign rank tests to compare BIS scores if variable transformations of BIS fail to induce approximate normality. We will not be specifically controlling for telemedicine vs face-to-face CBT but have planned subset analyses to see if differences exist based on method of CBT delivery.

11.b. Power Analysis/Sample Size Justification. Power analyses were performed using PASS 2008, version 08.0.13. Based on our preliminary data, we expect 35 patients/year to be eligible for the study, of

whom 84.6% will be 'somewhat likely' or 'highly likely' to participate in an intervention for their BID (unpublished data). Assuming that we enroll two-thirds of the eligible and 'likely to participate' subjects, if we enroll over 12 months, we would achieve our sample size of $n=20$.

The study seeks to characterize the effects of CBT on BID. **Figure 4** shows the power to detect absolute differences in BIS for $n=20$ based on a paired t-test with SD (BIS difference) = 3.8 (preliminary data), and two-sided $\alpha = 0.05$. We estimate power to be at least 80% to detect a difference in BIS scores of

approximately 2.5 or greater, a power estimate that is conservative given our proposed analysis plan using LME regression that borrows strength over time. In our preliminary data, we observed BIS differences of approximately 2 points before and after surgery without any intervention. We expect even larger changes in BIS based on the CBT intervention, which is reasonable to provide preliminary evidence of CBT efficacy for our sample of $n=20$.

11.c Data Analysis Plans for Secondary Endpoints.

Sociodemographic and oncologic variables will be summarized using descriptive statistics, including mean, median, standard deviation, interquartile range, and range for continuous variables, and frequencies and percentages for categorical variables.

Additional study variables, including: **shame and stigma scale score** (summed score ranging from 0 to 80); PROMIS measures of **depression, anxiety, social roles, and isolation** (summed scores each ranging from 0 to 16); and **head and neck performance status** (summed score ranging from 0 to 100), will be summarized using descriptive statistics. Additionally, we will evaluate the association between each of these study variables and response to CBT. Specifically, we will examine the association between change in BIS ($\Delta\text{BIS}_1 = 1$ month post-CBT versus baseline; and $\Delta\text{BIS}_3 = 3$ month post-CBT versus baseline) and each variable using Spearman's correlation coefficient.

Response variables (in addition to **Figure 4: Power to detect change in BIS for a sample size of 20 based on a paired t-test with two-sided $\alpha = 0.05$ [SD(BIS difference) = 3.8].** (summed score ranging from 0 to 80); **body image coping** (summed score ranging from 35 to 140). De... and neck cancer QoL (summed score ranging from 35 to 140). De... summarize each variable at each time point. We will also examine the association between change in BIS and each variable using Spearman's correlation coefficient. Finally, we will evaluate the effect of CBT on each response variable using the LME regression model approach described in Section 11.a.

CBT utilization patterns and **caregiver/dyad CBT feasibility data** will be summarized using descriptive statistics.

11.d. Steps to Maintain Confidentiality. To help protect participant confidentiality, we will assign a unique study ID number to each subject's information in place of his/her name and will label data collection forms with the ID number. All hard copy and electronic files will be stored appropriately using double-locked methods and password-protection. Only the study team member will have access to study records. Participant data will be collected and recorded on either a password-protected electronic data capture format (REDCap) or paper-based forms depending upon patient preference. For the paper collection data method, the data collection form will be labeled only with the participant's unique study ID number, and then stored within locked drawers in a locked office. The information on these paper forms will be transferred to a password-protected REDCap database such that all data will be stored in the password-protected REDCap Database. Only members of the study team will have access to the data. We have no plan to use laptops, jump drives, CDs/DVDs to transport data.

11.e Quality Control of Collected Data. The PI will meet with the study coordinator once each month to review the quality of the collected data, assessing for missing data, internally inconsistent data, other data irregularities, progress towards enrollment.

12.0 Provisions to Monitor the Data to Ensure the Safety of Subjects (if applicable)

12.a.1. Identification of risks and plans to minimize risk.

Expected Risks related to cognitive behavioral therapy	Frequency

 Emotional distress/discomfort 	 Occurs frequently,  Occurs infrequently  Occurs rarely  Frequency unknown

 frustration 	 Occurs frequently,  Occurs infrequently  Occurs rarely  Frequency unknown

12.a.2. Criteria below under which an individual subject's study treatment or study participation would be stopped or modified. At subject, PI, or study team member request.

12.a.3. Criteria under which the entire study would need to be stopped. Per IRB or PI discretion.

12.a.4. Reporting of subject withdrawals/dropouts to the IRB prior to study completion. Via IRB annual continuing renewal submission.

12.b. Definition of Adverse Events and Protocol Deviations.

12.b.1. Definition of adverse events (AE) for this study. Any undesirable sign, symptom or medical or psychological condition that is related to the study intervention (cognitive behavioral therapy).

12.B.2 Definition of serious adverse event. A serious adverse event will be considered any undesirable sign, symptom, or medical condition which is fatal, is life-threatening, requires or prolongs inpatient hospitalization, results in persistent or significant disability/incapacity, constitutes a congenital anomaly or birth defect, is medically significant and which the investigator regards as

serious based on appropriate medical judgment. An important medical event is any AE that may not result in death, be life-threatening, or require hospitalization but may be considered an SAE when, based upon appropriate medical judgment, it may jeopardize the patient and may require medical or surgical intervention to prevent one of the outcomes listed in the definitions of SAEs.

12.b.3 Definition of an unanticipated problem. An unanticipated problem is any event, experience that meets ALL 3 criteria below (*see MUSC IRB policy HRPP 4.7*):

- is unexpected (in terms of nature, severity, or frequency) given: (a) the research procedures that are described in the protocol-related documents, such as the IRB-approved research protocol and informed consent document; and (b) the characteristics of the subject population being studied;
- is related or possibly related to a subject's participation in the research; and
- suggests that the research places subjects or others at a greater risk of harm (including physical, psychological, economic, or social harm) related to the research than was previously known or recognized.

12.b.4 Definition of a protocol deviation. A protocol deviation is any variance from the protocol involving a subject or subjects that is not approved by the IRB prior to its initiation or implementation, and occurs when a member of the study team departs from the IRB-approved protocol in any way without the investigator first obtaining IRB approval (*See MUSC IRB Policy HRPP 4.14*).

12.c. Adverse Event / Unanticipated Problem Recording and Reporting.

12.c.1. Inclusivity of adverse events collection. All AEs described above will be collected and reported.

12.c.2. Method of event data collection. Data collection will occur via electronic spreadsheet. The information will be saved in REDCap and managed by the study team.

12.c.3. Adverse Event classification. AE classification will occur using NCI Common Toxicity Criteria, Version 4.0.

12.c.4. Relationship of adverse events to study participation. The PI will specify the following relationship of AEs to study participation:

- | | |
|-----------|---|
| Definite: | AE is clearly related in time and a direct association can be demonstrated to the study intervention |
| Probable: | AE is reasonably related in time and is more likely explained by the study intervention than by other causes |
| Possible: | AE may be reasonably related in time and the AE can be explained equally well by causes other than the study intervention |

12.c.5. Timing of recording/reporting of adverse events/unanticipated problems.

Recording/reporting of AEs will begin after the subject signs informed consent and end after the subject completes the intervention and follow up period as defined in the protocol.

12.d. Data and Safety Oversight Responsibility.

12.d.1 Persons responsible for overseeing safety data. The PI will be responsible for overseeing safety data.

12.d.2. Content of aggregate reviews. Aggregate reviews will occur by the PI for all adverse events, unanticipated problems, protocol violations, audit results, early withdrawals, whether the study accrual pattern warrants continuation/action, and endpoint data.

12.d.3. Timing of aggregate reviews. Aggregate reviews will occur monthly.

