Data from our ongoing research show 85.7% of surgically-treated HNC patients have BID at 1 month postoperatively. 69.6% of these patients report being “likely” or “highly likely” to seek treatment for BID if it were available. Effective treatments for HNC patients with BID remain unknown; however prior work has demonstrated that CBT is an effective intervention for a multitude of psychological and behavioral concerns. Therefore, we will complete a single-arm, phase II pilot study of time-limited CBT on BID in patients with surgically-treated HNC. Reliable, validated PRO measures of BID will be collected before, 1 month and 3 months after the CBT intervention to provide preliminary data on the effectiveness of CBT for BID in patients with surgically-treated HNC, addressing this critical knowledge gap. We expect that time-limited CBT implemented in the post-treatment period will decrease BID and improve QOL in affected patients.

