We also found that pre-operative PRO measures of depression, social satisfaction, social isolation, shame/stigma were associated with a BIS of ≥ 5 at 1 month after surgery (all $p < 0.05$); but that demographic and oncologic characteristics were not predictive (see **Table 2**).

Table 1: Univariate associations of demographic, oncologic, and psychosocial variables with 1 month post-operative body image scale scores.

Variable		1 month post op BIS < 5 (n = 14)	1 month post op BIS ≥ 5 (n = 14)	p-value [†]
Variable		Summary measure*	Summary measure*	p-value [†]
Age	median (IQR)	62.5 (53 – 71)	55 (42 – 59)	0.10
Race	White	11 (79)	11 (79)	>0.99
	Non-white	3 (21)	3 (21)	
Sex	Male	12 (86)	8 (57)	0.21
	Female	2 (14)	6 (43)	
Marital status	Married	9 (64)	5 (36)	0.13
	Non-Married	5 (36)	9 (64)	
BMI	median (IQR)	25.5 (21.0 – 26.9)	27.0 (21.2 – 35.7)	0.47
Reconstruction	Free Flap	4 (29)	5 (36)	>0.99
	Non-Free Flap	10 (71)	9 (64)	
Prior Head & Neck Cancer	No	7 (50)	6 (43)	>0.99
	Yes	7 (50)	8 (57)	
Pre-treatment PRO	Anxiety	9 (5 – 11)	10.5 (9 – 13)	0.13
	Depression	4 (4 – 6)	8 (6 – 13)	0.03
	Social Satisfaction	20 (16 – 20)	13.5 (9 – 16)	0.0035
	Social Isolation	4 (4 – 4)	7 (4 – 12)	0.0041
	Shame and Stigma	11 (5 – 14)	19.5 (17 – 34)	0.0091

Abbreviations: BIS = Body Image Scale; IQR = inter-quartile range; PRO = Patient-reported outcome

*Summary measures are median (IQR) for continuous variables, and frequencies (percent) for categorical variables.

†Wilcoxon rank-sum test for continuous variables; Fisher's exact test for categorical variables

HNC patients also expressed an interest in seeking treatment for their BID if it were available. Prior to surgery, 63.9% of patients reported that they were 'somewhat likely' or 'highly likely' to obtain treatment for their BID if it were available; this number increased to 69.6% at 1 month after surgery. **Our ongoing research provides novel preliminary data about risk factors for BID following HNC surgery, shows that BID increases in frequency after surgery, and confirms that it represents an area of unmet cancer care need.**

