3.b. CBT Intervention and Implementation. At the 1-month post-HNC treatment time point, patients with BID as determined by BIS score ≥ 5 will undergo time-limited CBT consisting of 5 weekly sessions. Each session will be guided by the HNC BID module that we develop (**C.2.b.4**) but customized to each patient's specific concerns⁴⁰. Each session will last ~60 minutes and be conducted one-one with [name], who will administer the CBT as part of clinical psycho-oncology care at HCC. Patients will complete questionnaires prior to CBT and 1 and 3 months after CBT (**Figure 4**). We considered alternate dose schedules of CBT but chose a 5-week schedule because evidence suggests that brief (e.g. 5-week) CBT reduces anxiety and depression and improves QOL in cancer patients⁵⁸. To overcome the expected travel distance-related barrier to receipt of CBT (**2.8**), we will offer the option of home-based, telemedicine CBT through an existing MUSC program⁵⁹. This will consist of one CBT session at HCC followed by iPad-based, tele-CBT for the next 4 sessions. Patients will receive the iPad and brief training session from MUSC Center for Telehealth staff at the in-person CBT session. They will take the iPads home, use them for the next 4 tele-CBT sessions, and mail them back to MUSC at the study conclusion. This strategy, which has been successfully piloted at MUSC⁵⁹, addresses the fact that most telehealth usability issues, especially in geriatric patients, occur during initiation⁴³. Introducing a second method of delivering CBT (i.e. telehealth CBT vs in-person CBT) will complicate analysis of the effectiveness of CBT by increasing study heterogeneity. However, we expect that this analytic challenge will be outweighed by the increased enrollment related to telehealth CBT for those who cannot travel to HCC for weekly CBT.

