6.0 Number of Subjects

It is expected that we will enroll 20 subjects in the study.

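### Does the 12-month accrual forecast in section 11.b fail because other sections report 69.6% willing patients rather than 84.6%?

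*Protocol*

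**What the plan says.** Section 11.b builds the accrual forecast from three inputs. The first is the yearly supply: "Based on our preliminary data, we expect 35 patients/year to be eligible for the study". The second is willingness among those eligible patients, "whom 84.6% will be 'somewhat likely' or 'highly likely' to participate in an intervention for their BID (unpublished data". The third is an openly stated assumption that two-thirds of the eligible and willing will enrol. The conclusion is that "if we enroll over 12 months, we would achieve our sample size of" 20.

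Two earlier sections give a lower willingness. Section 1.0 states: "Data from our ongoing research show 85.7% of surgically-treated HNC patients have BID at 1 month postoperatively. 69.6% of these patients report being"; the sentence concerns how probable it is that they would look for treatment. Section 2.i says of those somewhat or highly likely to obtain treatment if it existed that "this number increased to 69.6% at 1 month after surgery".

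On who counts as having BID, section 3.b says that "patients with BID as determined by BIS score ≥ 5 will undergo time-limited CBT consisting of 5 weekly sessions", and section 10.b.2 repeats this. The table in section 2.i has a column headed "1 month post op BIS ≥ 5 (n = 14"), out of 28 patients. Section 6.0 sets the target: "It is expected that we will enroll 20 subjects in the study".

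**The concern.** The willingness figures in sections 2.i and 11.b use the same pair of answer categories and come from the same team, yet differ by 15 percentage points. Neither has a stated denominator and nothing explains the gap. If BID means a BIS of 5 or more, as section 3.b says, then section 1.0 attaches the 69.6% to exactly the patients who would be eligible, and section 11.b seems to use a different figure for the same group.

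The forecast also has no margin: 20 is reached only by rounding up 19.7. The 20 enrolled patients are the same 20 pairs on which the power statement rests. If the lower figure were right and enrolment ended at 12 months, the trial would have about 16 patients and less power than stated.

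**Working it through.** **Inputs.** 35 eligible per year, 84.6% willing and two-thirds enrolled (section 11.b); 69.6% (sections 1.0 and 2.i); n = 20, standard deviation of the BIS difference 3.8, two-sided alpha 0.05, paired t-test, difference of about 2.5 points (section 11.b).

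**1. The plan's own forecast.** Patients in 12 months = eligible × willing share × enrolled share.

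- 35 × 0.846 × 2/3 = 19.74, which rounds to 20.
- Time to 20 patients: 20 / 19.74 × 12 = 12.2 months.

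The forecast reproduces; there is no arithmetic error.

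**2. The same product with 69.6%.**

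- 35 × 0.696 × 2/3 = 16.24 patients in 12 months.
- Time to 20 patients: 20 / 16.24 × 12 = 14.8 months.
- Enrolled share needed for 20 in 12 months: 20 / (35 × 0.696) = 82%, against two-thirds assumed.
- Willingness needed for exactly 20 with the other inputs fixed: 20 / (35 × 2/3) = 85.7%; for 19.5 patients, 83.6%.

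The forecast is therefore sensitive to the willing share. The question is whether 69.6% belongs in it.

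**3. Do the two percentages describe the same patients?**

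- Section 11.b applies 84.6% to eligible patients. Section 5.c.1 defines eligibility as BIS ≥ 5 at 1 month after treatment.
- Section 1.0 attaches 69.6% to the patients with BID 1 month after surgery, and says these are 85.7% of the cohort. With the 28 patients of section 2.i that is 24 (24/28 = 85.7%).
- The table in section 2.i shows 14 of 28 (50%) with BIS ≥ 5 at the same time point. At least 24 − 14 = 10 of the patients counted as having BID were below the eligibility cut-off.
- The time points need not match. The 69.6% was taken 1 month after surgery; screening takes place 1 month after the end of treatment, which may include adjuvant therapy (sections 5.b and 5.c.1).
- The questions are worded differently: taking part in an intervention (section 11.b) against seeking or obtaining treatment were it available (sections 1.0 and 2.i).

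On these counts the 69.6% belongs to a wider and, on average, less affected group than the one that feeds the forecast. Greater willingness among the more affected is plausible and involves no contradiction.

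**4. Can the denominators be recovered?** Only by inference. With at most 28 respondents, 69.6% can only be 16/23, and 84.6% only 11/13 or 22/26. If 16/23 is right, at least 23 − 14 = 9 of the respondents had BIS below 5. If 11/13 is right, it would fit the 14 patients with BIS ≥ 5, and its exact 95% interval (54.6% to 98.1%) contains 69.6%. However, the preoperative 63.9% in section 2.i matches no fraction with a denominator up to 28 (the smallest is 23/36), so the willingness data may extend beyond the 28 patients. Nothing firm can rest on these fractions.

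**5. Power.** Exact paired t-test, noncentral t, for a 2.5-point difference:

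| Pairs | Power at 2.5 | Difference detectable with 80% power |
|---|---|---|
| 20 | 79.7% | 2.51 |
| 16 | 69.2% | 2.85 |

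The 20-pair row reproduces section 11.b. The 16-pair row applies only if 69.6% is the right rate and enrolment also stops at 12 months.

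**The case for a change.** The best argument for a change is that the different-groups explanation exposes a fault of its own. It works only if BID in sections 1.0 and 2.i means something other than BIS ≥ 5, whereas sections 3.b and 10.b.2 determine BID by that cut-off. Either the two willingness figures conflict or the term carries two meanings. In addition, the 84.6% is unpublished and has no denominator, the accrual assumption is part of the sample size justification and so is not something left to a statistical analysis plan, and the forecast is the only yardstick for the monthly accrual review.

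Part of this stands. The term is used loosely, and the source of 84.6% should have been given. But the table in section 2.i settles which reading fits the data: 85.7% and 50% cannot both be the share with BIS ≥ 5 in the same 28 patients. Eligibility itself is never in doubt, because section 5.c.1 states the cut-off as a number.

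The power argument does not stand. The 12 months is conditional wording, and no section closes enrolment at that point. The target is 20 in sections 6.0, 8.d and 11.b. Sections 11.e and 12.d call for monthly review of enrolment progress and of whether accrual warrants action, so a pace of 1.35 rather than 1.64 patients a month (16.24/12 against 19.74/12) would be watched from the start.

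**Conclusion.** No change is needed. Section 11.b reproduces from its stated inputs (19.7, rounded to 20). The 16.2 appears only when a percentage tied to a wider group is substituted, and the protocol does not show that this percentage applies to eligible patients. Nor does it prove that 84.6% is right: its denominator is not given, and the two-thirds uptake is an assumption in any case.

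If 69.6% did apply, enrolment would take about 14.8 months instead of 12.2, some 2.6 months longer, in a single-site pilot. Sample size, analysis and stated power would be the same. The fall to 69.2% power needs a stop at 12 months, which the protocol does not plan. The conclusion assumes that enrolment runs until 20 patients are in, as the target and the conditional wording imply. Giving the denominators and using one meaning of BID would make the section clearer but would alter no result.

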3.0 Intervention to be studied

3.a. Development of a CBT Module for HNC Patients with BID. Although extensive literature exists for implementation of disorder-specific CBT³⁹, no specific CBT modules for HNC patients with BID exist. Therefore a critical initial step is to establish a disorder-specific CBT intervention for HNC patients with BID. In conjunction with [name], [name] will develop a 5-week, CBT module for HNC patients with BID using CBT core components (i.e. psychoeducation, self-monitoring, and cognitive restructuring). The intervention will be informed by existing CBT from other body image disorder realms^{40,41}. The intervention

will contain population-specific components including identifying and modifying maladaptive beliefs about disfigurement and functional changes following surgery. It will address the multidimensional nature of BID in HNC patients⁶ and will seek to reduce avoidance behaviors, improve social support, and enhance adaptive stress management skills.

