4.0 Study Endpoints

4.a. Primary Endpoint

4.a.1. Body Image Disturbance. The primary outcome measure will be BID as measured by the Body Image Scale (BIS). The BIS has been validated in oncology patients¹³ and is the most widely used scale for BID in oncology⁶. It is a 10-item measure that is scored on a 4-point Likert scale; higher scores indicate greater body image dissatisfaction. It addresses the affective, cognitive, and emotional aspects of body image⁶⁰.

4.b. Secondary Endpoints.

4.b.1. Body Image Investment. Body image investment (i.e. the importance and influence of appearance) will be measured using the Appearance Schemas Inventory-Revised (ASI-R)⁶¹. This 20-item measure is scored using a 5-point Likert scale with greater scores indicating greater body image investment.

4.b.2. Body Image Coping. The Body Image Coping Strategies Inventory (BICSI) is a validated measure used to assess cognitive and behavioral responses to manage threats to body image⁶².

4.b.3. HNC QOL. We will employ the EORTC QLCC30/H&N35 module to evaluate QOL⁶³.

4.c. Exploratory Endpoints for Mediator Analysis. These following endpoints will be used to determine whether changes in BID over time as measured by the BIS are mediated through these variables. They will also be incorporated into a regression analysis to identify characteristics of sub-populations of patients who benefit from CBT for BID.

4.c.1. Shame and Stigma. The Shame and Stigma Scale is a 20-item, validated tool that measures shame with appearance, stigma, regret, and social/speech concerns in patients with HNC⁶⁴.

4.c.2. Depression and Anxiety. Patient-Reported Outcomes Measure Information System (PROMIS) measures of depression and anxiety will be employed. PROMIS measures are validated questionnaire developed by the NIH for evaluating health-related quality of life⁶⁵.

4.c.3. Social Roles and Isolation. Social roles and isolation will be assessed by PROMIS measures⁶⁵.

4.c.4. Head and Neck Performance Status and Function. Performance Status Scale for Head & Neck Cancer, which assesses performance in domains of eating, speech, and diet⁶⁶.

4.d. Exploratory Endpoints to Refine Study Intervention Design, Implementation, and Scalability

4.d.1. Caregiver/Dyad CBT Feasibility Data. We will collect these data for use in future studies based on prior work exploring couples-based CBT in breast cancer patients with BID⁶⁷.

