10.c.1.a Sociodemographics and Oncologic Details. Race, ethnicity, age, gender, marital status, living situation, educational attainment, employment, income level, health insurance, tobacco use, and alcohol consumption will be obtained using questions from the Behavioral Risk Factor Surveillance Survey⁷⁰. Severity of comorbidity will be determined by the Adult Comorbidity Evaluation-27 (ACE-27)⁷¹. Oncologic and treatment data will be prospectively gathered from the EMR using study-specific questionnaires (date of diagnosis and treatment, tumor site, clinical and pathologic AJCC TNM classification and overall stage grouping, surgery, radiation, and/or systemic therapy treatment details, presence/absence of tracheostomy/laryngectomy, enteral feeding tube, patterns of recurrence, survival, and new primaries).

10.c.1.b. Shame and Stigma. Shame and Stigma Scale is a 20-item, validated tool that measures shame with appearance, stigma, regret, and social/speech concerns in patients with HNC⁶⁴.

10.c.1.c. Depression and Anxiety. PROMIS measures of depression and anxiety will be employed. PROMIS measures are validated questionnaire developed by the NIH for evaluating health-related quality of life⁶⁵.

10.c.1.d. Social Roles and Isolation. Social roles and isolation will be assessed by PROMIS measures⁶⁵.

10.c.1.e. Head and Neck Performance Status and Function. Performance Status Scale for Head & Neck Cancer, which assesses performance in domains of eating, speech, and diet⁶⁶.

10.c.2. Outcome Measures

10.c.2.a Primary Outcome Measures.

10.c.2.a.1. Body Image Disturbance. The primary outcome measure will be BID as measured by the Body Image Scale (BIS). The BIS has been validated in oncology patients¹³ and is the most widely used scale for BID in oncology⁶. It is a 10-item measure that is scored on a 4-point Likert scale; higher scores indicate greater body image dissatisfaction. It addresses the affective, cognitive, and emotional aspects of body image⁶⁰. A limitation of the BIS as an outcome measure for studies of BID in oncology patients is that there is no validated, clinically meaningful difference in scale scores. This is despite its use in prior studies attempting to characterize the magnitude and prevalence of body image disturbance as a problem in these patients^{21,72}.

10.c.2.b. Secondary Outcome Measures.

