10.c.2.b.1. Body Image Investment. Body image investment (i.e. the importance and influence of appearance) will be measured using the ASI-R⁶¹. This 20-item measure is scored using a 5-point Likert scale with greater scores indicating greater body image investment

10.c.2.b.2. Body Image Coping. The BICSI is a validated measure used to assess cognitive and behavioral responses to manage threats to body image⁶².

10.c.2.b.3. HNC QOL. We will employ the EORTC QLCC30/H&N35 module to evaluate QOL⁶³.

10.c.2.c. Exploratory Outcome Measures.

[figure not shown]
10.c.2.c.1. Caregiver/Dyad CBT Feasibility Data. We will collect these data for use in future studies based on prior work exploring couples-based CBT in breast cancer patients with BID⁶⁷.

10.c.2.c.2. Qualitative Assessment of Experience with BID and CBT. To better understand the patient experiences with BID not captured in the questionnaires as well as their experiences with CBT, we will perform semi-structured exit interviews. Qualitative methods are essential to allow in-depth exploration of patient experiences⁶⁸ and guide intervention development for future studies⁶⁹. Participants will be asked to 1) discuss their preferences about the timing, format and content of the CBT sessions and 2) describe their program experiences and offer recommendations to improve delivery.

10.d. Data Collection:

10.d.1. Data Collection Timeline. The timeline for data collection is shown in **Figure 3**. We have protocols from our ongoing research to obtain data when study time points do not coincide with clinical care.

10.d.2. Data Collection Instruments. The self-administered PRO measures will be completed by patients electronically using an iPad (or paper format if requested) with assistance from the trained program coordinator as needed. A trained program coordinator will assist with data collection instead of a treating physician to minimize social desirability or attention seeking bias⁷³. The data instruments are uploaded into eIRB.

[figure not shown]

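### Section 11.c fixes body image coping as one summed score with no stated direction of benefit, although the CBT is meant to move coping responses in opposite directions, so effects on the total may offset.

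*Protocol*

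**What the plan says.** Body image coping is a secondary endpoint (Protocol 4.b.2 and 10.c.2.b.2), measured with the Body Image Coping Strategies Inventory (BICSI). The description of the instrument is brief: "The BICSI is a validated measure used to assess cognitive and behavioral responses to manage threats to body image". No subscales, reverse-scored items or favourable direction are given.

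Section 11.c fixes the score: "body image coping (summed score ranging from 35 to 140". It then puts that score to two uses:

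- a test of the intervention: "we will evaluate the effect of CBT on each response variable using the LME regression model approach described in Section 11.a"
- a correlation with change in the Body Image Scale (BIS): "We will also examine the association between change in BIS and each variable using Spearman's correlation coefficient"

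Sections 3.a and 10.b.1 state the aims of the CBT module: it "will seek to reduce avoidance behaviors, improve social support, and enhance adaptive stress management skills".

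For the primary measure the protocol does say what a high score means (10.c.2.a.1): "higher scores indicate greater body image dissatisfaction". It also says what a high score means for the body image investment measure. It does not do so for coping.

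**The concern.** By the protocol's own account, some responses to body image threats should fall under CBT (avoidance) and others should rise (adaptive skills). A single sum with no stated direction does not distinguish the two. A higher total could mean more avoidance or more adaptive skill, and a lower total is just as ambiguous.

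Both planned uses need a score whose sign has a meaning. The mixed-model contrast would show that the total went up or down, but not whether patients coped better. The Spearman coefficient with change in BIS has the same problem.

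If the total adds both kinds of item in the same direction, there is a second cost. A module that works as intended could leave the total nearly unchanged, and a null result would then say little about coping. Section 15.b says the study is to supply preliminary data for a randomized trial, so it matters which kind of coping moved.

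**Working it through.** **1. What the text settles without arithmetic**

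| Question | Where | Answer |
|---|---|---|
| How is coping scored? | 11.c | One summed score |
| Is that score tested for a CBT effect? | 11.c | Yes, mixed model, plus Spearman with change in BIS |
| What should CBT do? | 3.a, 10.b.1 | Lower avoidance, raise adaptive skills |
| Which direction of the total is better? | 4.b.2, 10.c.2.b.2, 11.c | Not stated |
| Does the inventory hold both avoidant and adaptive items, all scored upward? | 4.b.2, 10.c.2.b.2 | Not stated |

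The first four rows are enough to show that the total cannot be interpreted from this protocol. The fifth row is why offsetting can only be put conditionally.

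**2. The printed range**

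35 to 140 fits 35 items scored 1 to 4 (35 × 1 = 35; 35 × 4 = 140). The same range is also printed for quality of life, "and neck cancer QoL (summed score ranging from 35 to 140", in a sentence overrun by the Figure 4 caption. It cannot safely be assigned to the BICSI and is not used below.

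**3. The protocol's own power figure (11.b)**

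This is the only power statement in the protocol, and it concerns BIS. Inputs: n = 20, difference about 2.5, SD of the difference 3.8, two-sided alpha 0.05, paired t-test.

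- Noncentrality = 2.5 / (3.8/√20) = 2.94, with 19 degrees of freedom.
- Power from the noncentral t distribution = 79.7%, which agrees with the stated 80%.
- Standardized change = 2.5/3.8 = 0.66.

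**4. Illustration of offsetting, on assumed inputs**

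The protocol gives no effect size or SD for coping. Assume:

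- two equally weighted parts, avoidance and adaptive coping, each with SD of change 1;
- avoidance falls by d = 0.66 SD (borrowed from the BIS planning figure);
- adaptive coping rises by r × 0.66 SD;
- correlation ρ between the two changes from -0.3 to 0.3;
- n = 20, two-sided alpha 0.05.

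Net change in the sum = d(r − 1). SD of the change in the sum = √(2 + 2ρ). Standardized change in the sum = d(r − 1)/√(2 + 2ρ). For example, r = 0.5 and ρ = 0 give −0.33/1.414 = −0.233.

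| r | ρ = -0.3 | ρ = 0 | ρ = 0.3 |
|---|---|---|---|
| 0 (standardized change) | -0.558 | -0.467 | -0.409 |
| 0 (power on the sum) | 65.8% | 50.9% | 41.2% |
| 0.5 (standardized change) | -0.279 | -0.233 | -0.205 |
| 0.5 (power on the sum) | 22.0% | 16.8% | 14.0% |
| 1 (standardized change) | 0 | 0 | 0 |
| 1 (power on the sum) | 5% | 5% | 5% |

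Power on avoidance alone, at d = 0.66, is 79.9%. The 5% in the last row is the type I error rate, since the net change is zero.

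Under these assumptions the loss is large well short of exact cancellation. Even when only avoidance moves, adding a part that does not move costs power.

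**The case against.** The strongest objection is that offsetting depends on instrument content that the protocol does not show. It describes the BICSI as covering cognitive and behavioral responses, and that is not the same split as avoidant versus adaptive. There is no item list or scoring key, and the module's aims are not tied to particular items. This stands. A reader might infer that opposite effects do cancel in this total, but the documents do not support that. It would need avoidant and adaptive items added in the same direction, and complete cancellation would also need equal and opposite changes.

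Second, the magnitudes rest on assumed inputs: 0.66 is the BIS effect carried over to hypothetical coping parts. This also stands. The figures show how sensitive a mixed total could be and do not estimate this trial's power.

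Third, scoring direction is commonly left to a statistical analysis plan, and the protocol does not give a favourable direction for every other scale either. That would answer a complaint about missing detail alone. It does not answer this point, because 11.c makes a choice: it names a summed score and tests it, for a construct that the intervention is meant to move both ways.

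Fourth, the sentence in 11.c is damaged by the figure caption, and scoring text could have been lost. The words naming a summed score do follow directly on body image coping in an unbroken run, so that element is reasonably secure; the range is not.

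Finally, one might conclude that a total should never be analysed. The instrument's scoring rules are not in the document, so a flat ban goes too far.

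**Conclusion.** The point holds in limited form. The text supports this much: coping is fixed as one summed score, that score is tested for a CBT effect, the module aims to lower avoidance and raise adaptive skills, and no direction of benefit is given for the total. A change in it cannot be read as better or worse coping.

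That effects may partly or fully offset is a risk, conditional on the inventory mixing avoidant and adaptive items scored upward. Under the stated assumptions it could reduce power from about 80% for avoidance alone to somewhere between 66% and 5% for the sum, depending on how far adaptive coping rises and how the changes correlate.

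The primary BIS analysis and the sample size are not touched. This is a worthwhile correction to one of three secondary endpoints in a 20-patient single-arm pilot.

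**What to change.** In 11.c, make separate avoidance and adaptive coping scores the analysed coping endpoints, derived by the instrument's own scoring rules. State the expected direction of each (avoidance down, adaptive coping up), fit the mixed model of 11.a to each, and use the same scores in the Spearman analysis. Report a total only descriptively, and only if the instrument's rules define one. Add a line on score direction to 4.b.2 and 10.c.2.b.2, and restore the correct range for each scale in 11.c.

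The questionnaire, visits and sample size stay the same. The cost is a text edit and one or two more secondary contrasts, which add a little multiplicity at n = 20.
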